#### 9.3. Subject Consent

Subjects' legally authorized representatives will need to provide consent to participate in the study prior to any procedures specific to the study are undertaken. Subjects and/or LAR(s) will be provided with a description of the device and procedure; risks, benefits, and alternative procedures; length of participation required; method and amount of compensation, if applicable; and information regarding injury and confidentiality. Written and verbal communication will include non-technical language that is understandable to the subject(s)/LAR(s). Requirements for Informed Consent and, where applicable, Assent from the child will be per local IRB and regulatory requirements. The informed consent discussion(s) will only be conducted by the principal investigators (PIs) and/or his/her designee, provided they are trained in the study. Subjects and/or parent(s)/LAR(s) will be informed that their participation in this study is voluntary and they may refuse to participate or discontinue from the study at any time. PIs or designees will avoid any coercive language and at no time improperly influence or offer improper inducement of subjects to participate or continue participating in the study. At no time will any discussion or written language waive or appear to waive the subject's/ LAR's legal rights. Subjects and parent(s)/LAR(s) will be given ample opportunity to consider the study, read the informed consent form, and ask the investigator questions so that they are adequately informed about the research. Subjects/ LAR(s) will also be informed that after the investigation visits are completed, the subjects will receive the standard medical care, just as they would have, had they not participated in the study. The informed consent form must be personally signed and dated by subject and/or parent(s)/LAR(s) and investigator at time of consent. Additionally, assent forms will be completed and signed as applicable per IRB requirements. The informed consent process will be documented in the source records and a copy of the consent will be provided to the subject and/or parent(s)/LAR(s).

If new information becomes available that may affect a subject's and/or and parent(s)/LAR(s)'s decision to continue to take part in the study, this information will be discussed with the subject and LAR(s) by the investigator and new consent will be obtained in writing. The informed consent form must be personally signed and dated by subject and/or LAR(s) and investigator at time of consent. The informed consent process will be documented in the source records and a copy of the consent will be provided to the subject and/or and LAR(s).

#### 9.4. Randomization and Treatment Assignment

No randomization will occur during the course of the study.

#### 9.5. Medication Compliance

Compliance to the recommended standard of care will be monitored via the at home patient diary. Variations in standard care and patient departures from the standard of care will be recorded and considered in the analysis, but will not be considered a protocol deviation.

MDT17024BZP

Version 5.0 (18 MAR 2019)

Page 26 of 47

Medtronic

#### 9.6. Assessment of Efficacy

Intra-operative blood loss, procedure time, ability to dissect tonsil, ability to achieve hemostasis, analgesic consumption and post-operative pain level will be recorded in the eCRF and used to assess efficacy of the BiZact™ device.

#### 9.7. Assessment of Safety

Safety will be assessed by monitoring the occurrence of adverse events (AEs), serious adverse events (SAEs), death, adverse device effects (ADE), unanticipated serious adverse device effects (USADE), device deficiencies or the presence of localized infection as defined in Section 10. Assessments will take place starting during the procedure as soon as the device is in contact with the subject, through post-operative day 28 (+7) and will be recorded in the eCRF.

#### 9.8. Recording Data

This study will utilize an electronic database and eCRF. All data requested on the eCRF are required. Study visits or measurements not collected and/or recorded will be considered deviations unless otherwise specified. Generally, a source document will be generated for any clinical data points that are required for the study. However, there may be data such as the generation of subject ID, and certain aspects of the Adverse Event (AE) information (e.g. date reported, investigator evaluation) which may be considered as source. The Principal Investigator or authorized designee(s) must ensure the accuracy and completeness of the recorded data and then provide his/her electronic signature on the eCRFs. The Investigator's electronic signature for specific eCRFs will be documented in compliance with local regulations and compliance with the protocol. Changes to data previously submitted to the sponsor will require a new electronic signature by the Investigator to acknowledge/approve the changes.

#### 9.9. Deviation Handling

A study deviation is an event where the Investigator or site personnel did not conduct the clinical study according to the Clinical Investigational Plan or Clinical Investigation Agreement. The Investigator is not allowed to deviate from the above-mentioned documents except under emergency circumstances to protect the rights, safety and well-being of human subjects.

No changes to the protocol will be permitted without the written approval from Medtronic, the IRB/EC and applicable Competent Authority. The investigator must notify Medtronic and the reviewing IRB/EC of any deviation from the Investigational Plan when specific to the protection of the life or physical well-being of a subject in an emergency. The deviation will be recorded in the eCRF and such notice must be given as soon as possible, but in no event later than five (5) working days after the emergency has occurred. Except in such an emergency, prior written approval by Medtronic is required for changes in or deviations from the Plan. If these changes or deviations affect the scientific soundness of the Plan or the rights, safety, or welfare of human subjects the IRB/EC will also be notified. All other deviations will be reported per the site's IRB/EC standard operating procedures. Should any deviations from the Investigational Plan occur, these will be reviewed by Medtronic for their clinical significance and compliance to the protocol. Repetitive or serious investigator compliance issues may result in the need to initiate a corrective action plan, and in some cases, freeze enrolment or ultimately terminate the Investigator's participation in the clinical study.

MDT17024BZP

Version 5.0 (18 MAR 2019)

Page 27 of 47

Medtronic

If any Medtronic representative discovers that an investigator is not complying with the signed Investigator Agreement, the investigational plan, applicable laws, or any conditions of approval imposed by the reviewing IRB/EC, they will report to the clinical study manager and take such steps necessary to promptly secure compliance. If compliance cannot be secured, device shipments to the investigator may be discontinued and the investigator's participation in the investigation terminated. Medtronic shall also require such an investigator to dispose of or return the device, unless this action would jeopardize the rights, safety, or welfare of a subject.

#### 9.10.Subject Status

#### 9.10.1. Screened Subjects

Subjects who are being evaluated for eligibility in the study are considered screened or being screened.

#### 9.10.2. Screen Failures

Subjects whose LAR(s) provide study consent, but then are determined to be ineligible to participate prior to the procedure will be considered screening failures and will not require additional study follow-up visits. The reason for the screening failure will be clearly delineated on the applicable CRFs. If a subject is being screened to participate and the cohort closes during the screening period (see section 9.10.1), the subject should be withdrawn by the investigator, and he/she will not receive the surgery with the device.

#### 9.10.3. Enrolled Subjects

A subject is considered enrolled in the study when the subject's LAR signs the consent. Data will not be captured until the subject is determined to be eligible and the tonsillectomy has begun (Day 0). As soon as the tonsillectomy surgical procedure has begun and the BiZactTM device has been in contact with the subject, the subject must be followed. Subjects who are enrolled, but discontinue the study for any reason prior to the start of the tonsillectomy procedure or usage of the study device, will not be followed unless they are later able to complete the tonsillectomy, See section 9.10.4. These subjects will not count towards the 60-subject enrollment for the study, nor towards the site enrollment maximum (36). In all subject cases where the device was in contact with the subject will be included in the intent-to-treat (ITT) population. The per-protocol population will consist of subjects in the ITT population that did not have a major protocol deviation.

#### 9.10.4. Subject Withdrawal or Discontinuation

Subjects for whom consent has been obtained and are deemed eligible, but later consent is withdrawn will be withdrawn from the study, and their enrollment will not count toward the study enrollment, nor the maximum site enrollment (36). In the event the subject/subject's LAR withdraws consent, the date of withdrawal will be documented.

Subjects whose tonsillectomy has been rescheduled, but still wish to participate may participate if the dates of consent and screening are within 30 days of the new planned tonsillectomy date. If the new tonsillectomy date is more than 30 days after date of screening and/or consent, subjects / LAR(s) who wish to participate should be re-consented and re-screened. In this circumstance, this would be considered a new subject, and the previous consent and screening materials will be considered as a "withdrawn" subject.

MDT17024BZP

Version 5.0 (18 MAR 2019)

Page 28 of 47

Medtronic

If the surgeon has begun the tonsillectomy procedure with the intention of using the investigational medical device, but does not perform the procedure with the investigational medical device for any reason, that subject will not be included in the study nor will their enrollment count toward the maximum number of subjects per site or the total of sixty (60) subjects for the final analysis (section 13.3 Analysis Population). Only procedures where the investigational medical device has come in contact with the subject will be included in the study analysis (see sections 9.10.3 and 13.3 ITT population). If the tonsillectomy procedure has begun, but the investigational device is not used (e.g. generator failure), the subject will be removed from the study, and the reason will be document, including any device deficiencies.

The reason for study exit will be documented on the applicable electronic case report form (eCRF). If the Study Investigator voluntarily removes a subject from further study participation prior to the surgery, supporting documentation must be in place for the rationale and date of removal. Follow-up of subjects withdrawn or discontinued after the surgical procedure will be determined by surgeon, but will respect the rights and wishes of the subject. Every attempt will be made to contact subjects that are noncompliant with study procedures. Subjects will be considered lost to follow-up once the following steps have been taken:

- Two phone calls should be made to the subject/LAR(s). Each attempt should be clearly documented in the source documents and the response or lack thereof should be captured.
- If there is no response to the phone calls, then an official, certified letter should be written to the subject/ LAR(s). A copy of the letter and return or delivery receipts should be retained in the subject's source document.
- Additionally, the site should attempt to reach out to the primary care practitioner to determine the status of the subject and document this in the eCRF.
- When all due diligence attempts to contact have been made, after a period of two (2) weeks, the subject will be considered Lost to Follow-up. The Sponsor should be notified and the End of Study (EOS) form should be completed.

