## 13.2. Sample Size Determination

The analysis technique will be a 1-sample t-test (or Wilcoxon ranked sign if nonparametric test is desired), with a one-sided type I error rate ( $\alpha$ ) of 0.025. A sample size of 60 subjects is selected to ensure that multiple surgeons participate and to create an opportunity for a range of subject ages to be enrolled. Statistical power for a sample size of 60 subjects exceeds 99%.

MDT17024BZP

Version 5.0 (18 MAR 2019)

Page 38 of 47

Medtronic

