## 13.3. Analysis Population

The intent-to-treat (ITT) population will consist of all enrolled subjects in the study who have undergone tonsillectomy and had contact with the BiZact™ device. The endpoint analyses based on the ITT population will be considered the principal analyses.

The per-protocol (PP) population will consist of all patients in the ITT population who do not have a major protocol violation. Analyses on the PP population will provide supporting evidence to the primary results.

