## 13.4. Statistical Analysis Endpoints

### 13.4.1. Primary Endpoint

The primary hypotheses of this study are:

H0: Mean intra-operative blood loss =31 mL HA: Mean intra-operative blood loss < 31 mL

The analysis technique will be a 1-sample t-test, with a one-sided type I error rate ( $\alpha$ ) of 0.025. If intraoperative blood loss data appear to be non-normally distributed (as evidenced by p < 0.05 from a Shapiro-Wilk test), a Wilcoxon signed rank test will also be conducted.

The performance goal of 31 mL derives from a meta-analysis comparing modern technology-assisted to conventional tonsillectomy (i.e. electrocautery and cold steel) (7). This paper included a total of 3,139 patients included in thirty-three published studies. The values from the studies that reported intra-operative bleeding were combined to calculate a mean blood loss. This value encompasses a variety of techniques and technologies and a number of different studies to capture a realistic value for comparison.

Intra-operative blood loss during tonsillectomy with BiZact™ is expected to be low. The expected mean value for the BiZact™ device is a conservative estimate derived from data for LigaSure™ and other vessel sealing systems in the Alexiou meta-analysis (7). The expected standard deviation is the average of the standard deviation values for all studies that reported blood loss in the meta-analysis.

Expected mean intra-operative blood loss for BiZact™: 10 mL Expected standard deviation: 15.1 mL

Additionally, descriptive statistics for blood loss will be reported for different age groups (ages 2-5 and ages 6-12) as well as for different sites, surgeons, and countries.

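### The set labelled intent-to-treat is a device-contact set: non-use of BiZact before contact enters no planned rate, and the consent-withdrawal rule has no time limit

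*Combined protocol and SAP*

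**What the plan says.** **Exclusion after surgery has begun.** Section 9.10.4 provides that when a surgeon has started with the intention of using BiZact "but does not perform the procedure with the investigational medical device for any reason, that subject will not be included in the study". The child counts neither toward the site maximum nor toward the sixty for the final analysis. The following sentence restricts the analysis to cases with device contact, with cross-references to 9.10.3 and 13.3. The section then adds: "If the tonsillectomy procedure has begun, but the investigational device is not used (e.g. generator failure), the subject will be removed from the study". The reason must be documented, along with any device deficiency.

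**Analysis set.** Section 9.10.3: "In all subject cases where the device was in contact with the subject will be included in the intent-to-treat (ITT) population". Section 13.3: "The intent-to-treat (ITT) population will consist of all enrolled subjects in the study who have undergone tonsillectomy", with device contact as a further condition. Section 13.3 makes analyses on this set the principal ones.

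**After contact.** Section 8.2 requires follow-up once the device has touched the child, even if the procedure is not completed with it. Section 9.1.2 records any alternative device, its operating time, the tonsil side and the reason.

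**Consent withdrawal.** For eligible subjects who later withdraw consent, 9.10.4 says "their enrollment will not count toward the study enrollment, nor the maximum site enrollment (36". It does not say whether this means before surgery only.

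**Rates planned.** The secondary endpoints (5.2.2, 13.4.2) and the safety proportions (13.5) include no quantity whose denominator is procedures attempted.

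**The concern.** Intent-to-treat normally tells a reader that nobody was dropped because of what happened after treatment was intended. Here a child in whom intended use had begun, and who could not be treated with the device, leaves the study, and another child fills the place.

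Such a case bears on the study's stated objective of safety and performance. BiZact works only with a compatible generator that recognises it (7.1, 7.6), and 11.5 counts reliability and malfunction among device deficiencies. The case nevertheless drops out of the denominator for hemostasis without other interventions and produces no rate of its own. Because the data are intended to support a pediatric indication (4.2), the reader should be able to see how often intended use did not take place.

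The consent clause raises a separate problem. Without a time limit, a child already treated who withdraws during follow-up is uncounted under 9.10.4 but belongs to the principal set under 9.10.3.

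**Working it through.** **Step 1. Where each case goes.**

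| Case | Governing text | In the set labelled ITT? | Enters a planned rate? |
|---|---|---|---|
| Device completes the procedure | 9.10.3, 13.3 | Yes | Yes |
| Contact, then another device or conversion | 8.2, 9.10.3, 9.10.4 contact sentence | Yes | Yes |
| Surgery begun, device never used | 9.10.4 | No, and not in the 60 | No; reason and deficiency recorded only |
| Treated, consent withdrawn later | 9.10.4 against 9.10.3 | Yes by 9.10.3; uncounted by 9.10.4 | Unclear |

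**Step 2. The plan's own figure.** Inputs from 13.2 and 13.4.1: n = 60, "one-sided type I error rate ( $\alpha$ ) of 0.025", "HA: Mean intra-operative blood loss < 31 mL", expected mean 10 mL, SD 15.1 mL.

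- Noncentrality = (31 − 10)/15.1 × √60 = 10.77 on 59 degrees of freedom. Power is above 99.99%, so the stated figure of more than 99% reproduces.
- With SD 15.1, success needs an observed mean below 31 − 2.001 × 15.1/√60 = 27.1 mL.

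**Step 3. Could the exclusion change the primary result?** The number of excluded procedures and their blood loss are not in the documents, so both are assumed. Add k procedures with loss L mL each to 60 cases with mean 10 and SD 15.1:

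- N = 60 + k
- m = (60 × 10 + k × L)/N
- v = [59 × 15.1² + 60(10 − m)² + k(L − m)²]/(N − 1)
- t = (31 − m)/√(v/N)

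Example, k = 6 and L = 60: m = (600 + 360)/66 = 14.55, √v = 20.41, t = 6.55, p = 5 × 10⁻⁹.

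| L (mL) | k = 1 | k = 3 | k = 6 | k = 10 |
|---|---|---|---|---|
| 31 | 10.3 | 11.0 | 11.9 | 13.0 (p = 2 × 10⁻¹⁴) |
| 60 | 10.8 | 12.4 | 14.5 | 17.1 (p = 1 × 10⁻⁶) |
| 100 | 11.5 | 14.3 | 18.2 (p = 0.0004) | 22.9 (p = 0.027) |

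Entries are means in mL. The test is lost only with about 10 excluded cases at 100 mL or about 27 at 60 mL, and never at 31 mL. Section 13.4.1 adds that for non-normal data "a Wilcoxon signed rank test will also be conducted". That test needs individual values and was not recomputed.

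**Step 4. Hemostasis without other interventions.** The proportion is s/(60 + k), where s is the number of successes among 60 contact cases and k the number of failures before contact, with Clopper-Pearson 95% limits. Both s and k are assumed.

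| k | s = 60 | s = 57 | Non-use k/(60 + k) |
|---|---|---|---|
| 0 | 100% (94.0–100) | 95.0% (86.1–99.0) | 0% |
| 1 | 60/61 = 98.4% (91.2–99.96) | 57/61 = 93.4% (84.1–98.2) | 1.6% (0.04–8.8) |
| 3 | 60/63 = 95.2% (86.7–99.0) | 57/63 = 90.5% (80.4–96.4) | 4.8% (1.0–13.3) |
| 6 | 60/66 = 90.9% (81.3–96.6) | 57/66 = 86.4% (75.7–93.6) | 9.1% (3.4–18.7) |

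The shift is about 2 to 9 percentage points for 1 to 6 excluded procedures.

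**The case against.** A reader might infer that the performance results exclude device failures in general, or that the set is conditional on the device having worked. The documents do not support that. The condition is contact, not success: an inadequate seal, rescue with another device and conversion all stay in the set. Nor does the phrase about any reason in 9.10.4 clearly drop a converted case, since the next sentence, 8.2 and 9.10.3 all point to inclusion. That wording needs tidying, but it does not exclude converted cases.

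A reader might also infer that treated children who withdraw consent are removed from the analysis. The clause concerns enrollment counts, 9.10.3 limits its own uncounted group to those who stop before surgery or device use, and 9.10.4 elsewhere treats withdrawal after surgery separately. What stands is an ambiguity that conflicts with 9.10.3 on a literal reading.

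Further points on the other side:

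- Failures before contact are not hidden. Sections 9.10.4, 11 and 11.5 require them to be documented. This stands, but recording is not a planned rate.
- Section 7.1 assigns 120 units, or 120/60 = 2 per planned subject, so a faulty unit could be replaced during the case. The only example of removal is generator failure, and the generator is separate equipment. This makes exclusions likely to be few.
- The affected endpoints are descriptive, with no hypothesis tests (13.4.2), and success rests on blood loss alone. This stands and limits the importance of the point.
- A device that was never used has no dissection rating, and the five-level scale has no failure category. Scoring non-use as failed hemostasis mixes equipment availability with tissue performance. This stands against making it the main analysis, but not against a sensitivity analysis.
- Section 13.8 refers to a separate SAP for full details. The combined document does not contain it, so a summary of attempted procedures there cannot be ruled out. The protocol wording would still need reconciling.

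**Conclusion.** The point holds in limited form. The principal set is a device-contact set under an intent-to-treat label. Procedures begun with intent to use BiZact in which it was never used are removed, not counted toward the 60, and enter no rate listed in the protocol.

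For blood loss a contact-based set is defensible, because a device that was never used cannot have caused the loss. Power is unaffected, and the conclusion would change only under extreme assumptions. The exposure is in secondary performance rates: about 2 to 9 points for hemostasis, if 1 to 6 failures before contact accompany 60 contact cases. Those counts are assumptions; the true number may be zero.

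The consent-withdrawal clause is a drafting conflict with 9.10.3 that should be resolved before it has to be applied. The changes are worth making because they cost little and use information the sites already document.

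**What to change.** 1. In 9.10.3, 9.10.4 and 13.3, rename the set *treated (device-contact) population*. Keep it for blood loss and as the main set for the other endpoints.
2. Define an *all attempted* set: every child whose tonsillectomy was begun with intent to use BiZact. Report the number, proportion and reasons for device non-use against it. Add a sensitivity analysis of hemostasis without other interventions that counts non-use for device or generator reasons as failure. Do not impute a dissection rating.
3. In 9.10.4, replace the phrase about any reason with a statement that the device never contacted the subject, to match 8.2 and 9.10.3.
4. Limit the uncounted consent-withdrawal rule to withdrawal before device contact. State that treated subjects who withdraw later stay in the analysis with the data collected up to withdrawal.

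The cost is protocol and SAP wording and one additional table. Reasons for non-use are already documented, so little or no new data collection is needed. Performance figures may look slightly less favourable.
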